1.6 Blinding of Main Study

The study is conducted in a blinded manner. All subjects, investigators, their clinical staff, the clinical coordinating center, the data management group, and the sponsor staff and delegates will

be blinded to the randomization codes. The local laboratories will also be blinded.

The IDMC reports and analyses for Closed Sessions will be organized by treatment arm ("unblinded"). In order to ensure confidentiality and minimize bias, the information will be provided to the IDMC by an unblinded statistician from a group that is independent of the sponsor and the blinded project team implementing the trial. A firewall will be maintained between the IDMC and statistician (unblinded) and the project staff (blinded). The IDMC will review safety data and other data as requested by the IDMC, in addition to the interim analysis results.

The person responsible for the study drug labelling will be unblinded, as will the independent statistical group preparing the reports for the IDMC. The person responsible for the data management group, who manages the programming of the randomization system will be unblinded. This individual will be the contact person if unblinding is necessary. This individual will not participate in data management and will only communicate unblinded data as set out below when contacted by the medical monitor.

Otherwise, randomization data will be kept strictly confidential, accessible only to authorized persons, until the time of unblinding after data lock at the time of interim analysis and at end of the study.

In case of emergency, a rapid unblinding procedure is available to investigators. If the investigator decides that the treatment code needs to be broken in the interest of subject safety, the investigator will have direct access to the study data management center to request unblinding of the specific subject. The data management center will respond in writing to the investigator only with the unblinded patient treatment allocation.

Only the investigator requesting the unblinding will receive the unblinding information. The investigator will promptly inform the Sponsor when a request to unblind is made and the circumstances involved. Any case that is unblinded in this way will be documented in a blinded manner in central study files.

1.7 Blinding of 1-year Follow-up Study

It is anticipated that a proportion of subjects enrolled in the Main Study will have reached their 1-year follow-up before the Main Study is unblinded. That proportion will depend on the rate of enrollment in the Main Study.

1.7.1 Subjects having the 1-year Follow-up While the Main Study is Blinded

Subjects whose 1-year follow-up occurs while the Main Study is still blinded will be contacted for telephone follow-up by study staff who are blinded to treatment allocation.

1.7.2 Subjects having the 1-year Follow-up After the Main Study is Unblinded

Subjects whose 1-year follow-up occurs after the Main Study is unblinded will be contacted for telephone follow-up by study staff who are firewalled from previous study staff who have become unblinded to treatment allocation. Specifically, such study staff will be firewalled from the Sponsor, the IDMC, the unblinded statistician, and the coordinating investigators.

1.8 Definitions

Baseline: A subject's baseline value for a given endpoint or parameter is defined as his/her latest measurement taken prior to study drug administration.

Prior and Concomitant Medications: Prior medications are defined as those taken within 24 hours prior to randomization. Concomitant medications are defined as those taken during study drug administration or after study drug has been administered through to Day 6 (or discharge). All prior and all concomitant medications will be recorded on the electronic case report form.

Randomization: The time of randomization is defined as the time randomization occurred on the central server and this time is considered time zero for the study. All time windows are calculated from the time of randomization.

Study Day: Day 1 is the date of randomization. As the study drug is intended to be administered as soon as possible after randomization (i.e., 15 minutes), this will also be the day of treatment initiation date. Study day is calculated relative to Day 1.

Treatment-Emergent Adverse Event: All AEs will be collected from the start of study drug administration until Day 30. All SAEs will be collected from the start of study drug administration until Day 90. A treatment-emergent adverse event (TEAE) is one that first occurs or worsens in severity or frequency after study drug administration has begun through to and including the Day 30. SAEs are collected through the last study visit. Those AEs that start at the same time and date as the study drug administration and those that first occur or worsen after the start of study drug administration will be considered TEAEs.

AEs with partial or missing dates will be handled as follows:

- If the start day and/or month of the AE is missing the AE will be considered treatmentemergent.
- If the start date is completely missing then the AE will be considered treatment-emergent.

2 ANALYSIS POPULATIONS

This study is designed to address a population of adults 18 years and older harboring an acute ischemic stroke who are selected for endovascular revascularization without intravenous or intraarterial thrombolytic therapy who will receive a single, 2.6 mg/kg (up to a maximum dose of 270 mg) intravenous dose of nerinetide or placebo.

2.1 This is a global trial being conducted under the same protocol at clinical sites in different countries in accordance with the national legislation of the country in which the trial is carried out. Following the completion of the study and provided that the requirements of 21CFR 312.120 are met, data from all study sites will be pooled for the purpose of analyses in this statistical analysis plan.Intent-to-Treat (ITT) Population

The primary efficacy analysis will be conducted on the ITT population, defined as all subjects randomized into the trial with grouping by randomized treatment, regardless of treatment actually received. Deceased subjects will be included in the ITT population with a mRS score of 6, NIHSS of 42 and Barthel Index of 0. An ITT analysis will also be conducted for the secondary endpoints, with subjects grouped according to the randomized (intended) treatment.

2.2 Safety Population

The safety population comprises all subjects receiving any amount of study drug. In safety analyses, subjects will be grouped according to treatment actually received.

2.3 Per Protocol (PP) Population

The primary analysis will be repeated on the Per Protocol (PP) population, defined to be all subjects randomized and treated, with no major protocol deviations. We define "major protocol deviations" as those with the potential to bias, confound, or otherwise obscure the treatment effect estimates or which involve ethical standards. This population will be determined via a blinded review of protocol deviations at the end of the trial before database lock and unblinding.

Missing data due to death during the study will not exclude a patient from the PP population (i.e. death is not considered a major protocol violation).

Prior to unblinding, the imaging from each subject at the time of inclusion will be adjudicated to determine whether they have met the criteria for endovascular intervention and the imaging inclusion criteria, and hence for the trial. This will include review of baseline NCCT, CTA and if performed CTP or MRP. Subjects who do not meet the imaging criteria outlined in the trial inclusion/exclusion criteria will be reviewed in a blinded fashion as described above to determine if they met the criteria.

Participants will be excluded from the per-protocol analysis for the following violations:

- did not meet inclusion/exclusion criteria,
- did not receive planned dose volume,
- incorrect study drug vial,
- infusion more than 15 minutes,
- consent not obtained (including incorrect Deferral of Consent where applicable).

3 STUDY ASSESSMENTS AND DATA COLLECTION

Study procedures and their timing are summarized in the Table 2: Schedule of Activities.

3.1 The Modified Rankin Scale

The primary endpoint used in this trial will be global disability, as measured by the mRS, at Day 90. The mRS is a valid and reliable clinician-reported measure of global disability that has been widely applied for evaluating recovery from stroke. It is a scale used to measure functional recovery (the degree of disability or dependence in daily activities) of people who have suffered a stroke^{9,10}. mRS scores range from 0 to 6, with 0 indicating no residual symptoms; 5 indicating bedbound, requiring constant care; and 6 indicating death.

The post dose mRS will be obtained at Day 6 (or discharge), Day 30 and Day 90 and at the One-Year follow up. Premorbid mRS status may be obtained at any time, but ideally at the Day 1 or 2 visit. The mRS will only be scored by those trained and certified (via

www.healthcarepoint.com) in the use of this scale. An Electronic Clinical Outcome Assessment (eCOA) tool may be used to conduct this assessment.

3.2 Mortality

Mortality status will be obtained at all visits during the 90-day study period and at the One-Year follow up. Specifically, it will be assessed at Day 6 or discharge and at Days 30 and 90. Mortality rate is defined as the number of deaths observed divided by the number of subjects observed over the 90-day study period between nerinetide and placebo control subjects.

3.3 Worsening of Stroke

Worsening of stroke is defined as (A) progression, or hemorrhagic transformation, of the index stroke as documented by medical imaging that is (a) life-threatening requiring intervention and/or (b) results in increased disability as gauged by a \geq 4 point increase from lowest NIHSS during hospitalization and/or (B) results in death from the index stroke.

3.4 National Institutes of Health Stroke Scale

The NIHSS is a standardized neurological examination score that is a valid and reliable measure of disability and recovery after acute stroke¹¹. Scores range from 0 to 42, with higher scores indicating increasing severity. The scale includes measures of level of consciousness, extra ocular movements, motor and sensory tests, coordination, language and speech evaluations. The NIHSS will be administered at Baseline, Post-EVT (2 Hours), Day 2, Day 6 (or discharge), Day 30 and Day 90. The NIHSS will only be scored by those trained in the use of this scale. An eCOA tool may be used to conduct this assessment. The NIHSS scores will be dichotomized into 0-2 (indicating a good neurological outcome) versus >2 (indicating otherwise).

3.5 Volume of Stroke

All subjects will undergo a follow-up brain MRI [including a minimum of axial DWI, gradientecho (GRE), FLAIR] at Day 2 (18 to 56 hours from the time of randomization). The Day 2 MR is considered a standard of care imaging procedure; if MR is unavailable, then NCCT is allowed. The Day 2 MR (and where MR is unavailable, CT) will be used to assess infarct volume. Infarct volume determinations will be conducted before database lock.

Version: 2.0	SAP NA-1-009
Date: 18 November 2021	NoNO Inc

Prior to database lock at 90 Days, the total volume of new strokes as measured by MRI or CT brain images (MRI preferred) in nerinetide versus placebo control participants will be calculated from the Day 2/3 imaging. Where MR is not available, infarct volumes will be determined from the Day 2/3 CT scan. The plan for combining CT and MRI data will be detailed in the Imaging Adjudication Charter.

3.6 Barthel Index

The BI is an index of functional independence¹² that is a valid measure of activities of daily living when employed in stroke trials¹³. Modified BI scores range from 0 to 100, with higher scores indicating greater independence in activities of daily living and mobility. The BI will be scored at Baseline (pre-morbid), Day 30 and Day 90 and at the One-Year follow up, by those trained in the use of this scale. Note that the original Barthel Index was a scale from 0-20. The modified Barthel index simply multiplies the original scale by 5 to provide a 100-point score. An eCOA tool may be used to conduct this assessment.

3.7 EQ-5D-5L

The EQ-5D-5L is a generic instrument for describing and valuing health. It is based on a descriptive system that defines health in terms of five dimensions: Mobility, Self-Care, Usual Activities, Pain/Discomfort, and Anxiety/Depression¹⁴. Each dimension has five response categories corresponding to: no problems, slight, moderate, severe and extreme problems¹⁵. The version of the instrument selected for the trial is interviewer administered either in-person, or by telemedicine or by telephone. The respondents will also rate their overall health on the day of the interview on a 0–100 visual analogue scale (EQ-VAS). The EQ-5D-5L will be administered at the Day 90 and at the One-Year follow up by those trained in the use of this scale. An eCOA tool may be used to conduct this assessment.

4 MISSING DATA AND DATA TRANSFORMATION

4.1 Statistical Methods

The software used for all summary statistical analyses will be SAS[®] (SAS Institute, Inc.) version 9.4 or later.

Unless otherwise noted, categorical data will be summarized for each treatment group using counts and percentages, with the denominator for percentages being the number of subjects in the population of interest. Unless otherwise noted, continuous data will be summarized for each treatment group using the number of observations (n), mean, standard deviation (SD), median, minimum, and maximum. Some continuous data will be reported as the median, interquartile range (IQR), minimum and maximum according to the clinical meaning of the data.

Percentages will be rounded to one decimal place, except 0% and 100% will be displayed without any decimal places. Minima and maxima will be rounded to the precision of the original value; means and medians will be rounded to one decimal place greater than the precision of the original value; standard deviations will be rounded to two decimal places greater than the precision of the original value. P-values will be reported to four decimal places (0.xxxx), with values less than 0.0001 presented as <0.0001.

Inferential analyses will generally include statistics such as 2-sided 95% confidence intervals (CI), and p-values.

The overall significance level for in this trial will be at two-sided 0.05. The type I error and the efficacy boundary for the final analysis will be adjusted accordingly based on the actual alpha spent at the interim analysis (details in Section 8).

In order to protect the overall trial false positive rate, the primary efficacy analysis and secondary outcome analyses will be analyzed in a fixed sequence, stopping and calling all subsequent analyses exploratory (and accepting the null hypothesis) at the first failed hypothesis test in the sequence. The fixed sequential order is:

- 1) Primary estimand
- 2) Secondary estimands, as specified in the order presented in Section 4.2.

4.2 Estimands

Death is an intercurrent event which may occur during the study. The fact that a participant has died may in itself be informative for quantifying the treatment effect, although data collections after death will not exist. Therefore, the primary and secondary estimands will be focusing on the composite strategy. More specifically, death will be incorporated as part of the primary and secondary estimands as described below and in Section 4.3.

The primary estimand will be the difference in the mRS response (i.e., mRS score of 0-2) proportions between treatment conditions (nerinetide vs. placebo) in the target patient population at Day 90. Deaths occurring over the Day 90 period will be considered as non-response.

The secondary estimands are defined below:

- The difference in mortality rate over the 90-day period between treatment conditions in the target patient population.
- The difference in worsening of stroke proportions between treatment conditions in the

target patient population over the 90-day period. Death meets the definition of worsening of stroke.

- The difference in showing a shift in mRS categories between treatment conditions in the target patient population at Day 90. Death occurring prior to Day 90 will be assigned with the worst mRS score (score of 6).
- The difference in NIHSS response (i.e., score of 0-2) proportions between treatment conditions in the target patient population at Day 90. Death occurring prior to Day 90 will be considered as non-response.

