- 3) Based on data from preclinical studies, the Phase 1 (protocol NA-1-001) safety trial, the Phase 2 ENACT trial²³ (protocol NA-1-002) and the Phase 3 ESCAPE-NA1 trial¹² (protocol NA-1-007), nerinetide is expected to be have an acceptable safety profile.
- 4) There is a compelling need to develop neuroprotectants in order to increase the proportion of patients who may benefit from EVT. These agents could improve the outcomes of patients and render more patients with AIS into candidates for endovascular or pharmacological recanalization treatment.

The current trial is intended to confirm the findings in the ESCAPE-NA1 study that nerinetide may improve functional independence, reduce mortality, and reduce infarction volumes in participants with AIS who are selected for EVT and who are not treated with thrombolytics. As such, it is a Phase 3, randomized, multicentre, blinded, placebo-controlled, parallel group, single-dose design. Participants harboring an acute ischemic stroke who are selected for endovascular revascularization without intravenous or intra-arterial thrombolytic therapy will be given a single, 2.6 mg/kg (up to a maximum dose of 270 mg) intravenous dose of nerinetide or placebo. Randomization will be stratified by time from stroke onset to randomization ≤ 4.5 hours (yes/no) and done with stochastic minimization to balance baseline factors within strata.

The current trial is timely, in that it is evaluating an intervention that may mitigate the detrimental effects of slowdowns in emergency stroke care workflows caused by COVID-19 (see Section 2.3.2). For example, if reperfusion is delayed by 30 minutes, the probability of a good outcome is reduced by $10.6\%^{24}$ and perhaps up to $26\%^{25}$. Treatment with nerinetide in patients who are not treated with thrombolysis improved good outcome by a similar degree in ESCAPE-NA1¹².

The main differences between this trial (ESCAPE-NEXT) and ESCAPE-NA1 are that:

- 1) ESCAPE-NEXT focuses on participants who do not receive thrombolysis, in order to confirm the results in that patient population observed in ESCAPE-NA1
- 2) The secondary outcomes in ESCAPE-NEXT focus on domains of clinical benefit other than functional outcome, namely mortality, rates of worsening of stroke and neurological function.
- 3) ESCAPE-NEXT has an analytic 1-Year follow-up sub-trial investigating the long-term effects of nerinetide treatment.

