1.2.2 Secondary Objectives

The secondary objectives are to determine the efficacy of nerinetide in:

- 1) Reducing mortality rate
- 2) Reducing worsening of stroke*
- 3) Reducing functional dependence
- 4) Improving neurological outcome

* Worsening of stroke is defined as (A) progression, or hemorrhagic transformation, of the index stroke as documented by medical imaging that is (a) life-threatening requiring intervention and/or (b) results in increased disability as gauged by a \geq 4 point increase from lowest NIHSS during hospitalization and/or (B) results in death from the index stroke.

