4.3 Missing Data

Every effort will be made to keep missing data, particularly the Day 90 outcome assessments, to a minimum. However, some missing data may be inevitable due to, for example, loss to follow-up.

All imputed values will be determined prior to database lock and conducting primary analyses via the rules documented prospectively in this Statistical Analysis Plan for the study.

To incorporate death as part of the estimand definition following the composite strategy, deceased participant will be assigned a score 6 on the mRS, 42 on the NIHSS and 0 on Barthel Index and be counted as non-responders. In addition, deceased participants are considered as experiencing worsening of stroke. Thus, there will be no missing mRS, NIHSS, BI or worsening of stroke data due to death.

No imputation is planned for safety data. Efficacy outcomes will be imputed using a datainformed imputation as follows:

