4.3.1 Imputation of Mortality and Worsening of Stroke

For the analysis of rate of mortality, for participants for whom the mortality status is not known at Day 90:

- if they were alive at Day 30, then the subject will be imputed as alive at Day 90
- if both the Day 30 and Day 90 mortality is status is missing, the participant will be imputed as Dead at Day 90.

Worsening of stroke data will be imputed similarly:

- if it's unknown whether the subject experienced worsening of stroke by Day 90 while they did not report any worsening of stroke by Day 30, then the subject will be imputed as not experiencing worsening of stroke at Day 90.
- if both worsening of stroke status is unknown at both Day 30 and 90, then the subject will be imputed as experiencing worsening of stroke at Day 90.

No imputation will be done on the missing one-year follow-up mortality data.

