6.2 Secondary Efficacy Estimand Analyses for Main Study

The primary analysis for the secondary estimands with binary endpoints will be based on the ITT population following the same methods as the primary estimand, and reported as described for each estimand including reporting by randomization strata if the interaction term in the GLM used for the primary pivotal analysis plus the interaction term is significant at the 0.05 level. Missing data will be imputed according to Section 4.3.

Binary secondary endpoints include: mortality rate, NIHSS responder and worsening of stroke.

For the secondary estimand of the "mRS shift analysis", the first step in the analysis will be an adjusted analysis with mRS score 5 and 6 combined, using a proportional odds model to derive the common odds of improvement ("shift") along the mRS scale. The mRS shift analysis will

only be conducted provided that the proportional odds assumption is found to be valid on testing. If it is found to be invalid, the remaining secondary endpoints will be deemed to be protected. Adjustment will include the same variables as the primary outcome analysis.

All tests will be conducted with two-sided level of significance alpha = 0.05 (overall for the in trial), adjusted for the interim analysis per the O'Brien-Fleming boundary spending function. A fixed sequence multiple testing procedure will control the overall experiment-wise error rate for the trial (see below). It pre-specifies that, with all tests conducted at the same pre-specified significance level, the primary endpoint will be tested first, and all subsequent tests are considered failed and deemed exploratory if conducted, in the order specified (primary analysis first, key secondary analysis second, etc.), after the first test which fails. All tests that follow the first failed test, are considered exploratory. The secondary endpoints, and the order they are to be tested, are as they are listed in Table 1: Objectives and Endpoints.

Sensitivity analysis of the secondary estimands will be conducted in ITT population with missing data not imputed.

Additional analysis details of each outcome along with the supportive analyses of the secondary estimands are specified in each section below.

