6.2.2 Worsening of Stroke

Worsening of Stroke is determined as the number of participants experiencing at least one worsening of stroke divided by the number of participants observed over the 90-day period in that treatment group, between nerinetide and placebo control participants. Results will be summarized and tabulated. The unadjusted logistic regression method will be used as a supportive analysis. The alpha protected secondary analysis of Worsening of Stroke as currently designed will also be supported by a further analysis in which the imaging requirement is waived, in order to include in this supportive analysis any cases in which the stroke worsened so rapidly that the patient was deemed palliative early on and did not undergo further imaging.

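### The SAP counts every death as worsening of stroke, but the written definition covers only death from the index stroke, so the endpoint tested is not the endpoint named

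*Combined protocol and SAP*

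**What the plan says.** Worsening of stroke is defined in the protocol synopsis, protocol 3.1.2 and 8.1.3, and SAP 1.2.2, the Table 1 footnote and 3.3. Limb (A) is imaging-documented progression or hemorrhagic transformation that is life-threatening and needs intervention, or that raises the NIHSS by at least 4 points. Limb (B), in all six places, applies only where the event "results in death from the index stroke".

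SAP 4.2 treats death as an intercurrent event and says that "the primary and secondary estimands will be focusing on the composite strategy". Under the worsening estimand it then says "Death meets the definition of worsening of stroke", with no reference to cause. SAP 4.3 turns this into a rule: "deceased participants are considered as experiencing worsening of stroke".

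SAP 6.2.2 describes the numerator as participants with at least one worsening and does not repeat the death rule. It calls the analysis alpha-protected and adds a supportive analysis "in which the imaging requirement is waived", to bring in patients who became palliative too early to be re-imaged. On testing order, SAP 6.2 says: "The secondary endpoints, and the order they are to be tested, are as they are listed in Table 1". Worsening stands there directly after mortality.

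**The concern.** A composite strategy changes the variable. Adding all deaths to a definition that admits only some of them gives a different endpoint: worsening of stroke or death from any cause. The SAP presents the addition as already contained in the definition and keeps the narrower name in Table 1, 3.3 and 6.2.2.

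What is at stake is the claim. Protocol 4.2 says the secondary outcomes "focus on domains of clinical benefit other than functional outcome, namely mortality, rates of worsening of stroke and neurological function", so mortality and worsening are offered as separate domains. Under SAP 4.3 every participant who dies is an event in both tests. If the primary and mortality tests succeed and this one follows, the reported reduction in worsening of stroke would rest partly on deaths that the definition excludes.

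**Working it through.** **Text check.** Take a participant who has no qualifying worsening and dies before Day 90 of a cause other than the index stroke.

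- SAP 3.3, limb (A): not met. Limb (B): not met. By definition a non-event.
- SAP 4.3: deceased, so an event.
- SAP 4.2: says the definition is met. It is not.

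Protocol 9.3.1 assigns deceased participants values on the mRS, NIHSS and Barthel Index and is silent on worsening. Protocol 9.3 gives the SAP precedence where the two differ, so SAP 4.3 settles that gap. It does not settle the mismatch above, which lies between sections of the SAP.

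**Size.** The plan gives no rate, effect or power for this endpoint, so there is no figure to reproduce. For scale only, mortality is taken from the no-alteplase stratum of the preceding trial (protocol 2.1.5): absolute reduction 7.5 points, relative reduction 39.7%.

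- Placebo mortality: 0.075 / 0.397 = 0.189
- Nerinetide mortality: 0.189 − 0.075 = 0.114

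Deaths at 850 participants (425 per arm), from unrounded rates:

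- 11.4% in both arms: 96.8
- earlier benefit recurs: 425 × (0.189 + 0.114) = 128.7
- 18.9% in both arms: 160.6

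Let f be the share of deaths not due to the index stroke; f is an assumption. At most f × deaths are classified differently. The bound is reached only if none of these participants had an earlier limb (A) event.

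| f | 11.4% both arms | benefit recurs | 18.9% both arms |
|---|---|---|---|
| 0 | 0 | 0 | 0 |
| 0.1 | 9.7 | 12.9 | 16.1 |
| 0.2 | 19.4 | 25.7 | 32.1 |
| 0.3 | 29.0 | 38.6 | 48.2 |

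At the interim (about 510 participants) expected deaths are 58.1, 77.2 and 96.3, so at most about 6 to 10 participants per 10% share.

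**Direction.** Assume that mortality benefit, that limb (A) adds 6% non-fatal events in each arm, and f = 0.2 of placebo deaths. Approximate power at two-sided 0.05, ignoring the interim, is Φ(|p1 − p2| / √(2p̄(1 − p̄)/425) − 1.96).

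- All deaths counted: 24.9% vs 17.4%, power 0.764.
- Index-stroke deaths only, other deaths equally frequent in both arms: 21.1% vs 13.6%, power 0.824.
- Index-stroke deaths only, other deaths reduced in the same proportion: 21.1% vs 15.1%, power 0.622.

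The count in SAP 4.3 can therefore weaken or strengthen the comparison. Limb (A) rates of 3% and 10%, with f from 0.1 to 0.4, give the same two directions.

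**The case against.** The strongest reply is that nothing is hidden. SAP 4.2 declares the composite strategy, 4.3 implements it, and a programmer following both would produce one event flag. The SAP also handles any-cause death compositely for mRS 0–2, NIHSS 0–2 and the Barthel Index without renaming those endpoints. No confirmatory test, p-value or testing order would change, so this is a one-line edit.

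Most of that stands: the rule is prospective and disclosed. The parallel with the scales is weaker, because death there takes a value on the scale and no cause-restricted definition is overridden. Nor does 6.2.2 read as if all deaths were already counted. It waives imaging to bring in early palliative cases, yet those who died by Day 90 are events under 4.3 anyway.

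A reader might also infer more than the documents support:

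- *Type I error is inflated.* It is not. The count is pre-specified and worsening is tested in a fixed sequence, only after the primary and mortality tests succeed.
- *Counting all deaths creates the overlap with mortality.* Only part of it. Limb (B) already includes index-stroke deaths, so some overlap exists under the written definition.
- *The protocol definition overrides the SAP count.* Protocol 9.3 says the reverse.
- *Deaths imputed under SAP 4.3.1 add to the problem.* The rule that "the participant will be imputed as Dead at Day 90" is written for the mortality analysis; worsening has its own imputation rule in the same section.

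**Conclusion.** The point holds as a mismatch between definition, name and count within the SAP. The sentence in 4.2 is wrong as written, and the endpoint tested is worsening of stroke or death from any cause under a narrower name. This should be corrected, because the endpoint is alpha-protected and its name would carry the claim.

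The size is bounded but not known: at most about 10 to 16 participants per 10% share of deaths not due to the index stroke at 850 participants, and none if that share is zero. This rests on assumed mortality of 11.4% to 18.9% and on no earlier qualifying worsening among those who died. The documents do not support a claim of bias for or against nerinetide.

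**What to change.** Before the interim unblinding:

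1. Keep the SAP 4.2/4.3 counting rule for the alpha-protected test.
2. Replace the 4.2 sentence with: *death from any cause is counted as an event under the composite strategy*.
3. Name and define the endpoint as *worsening of stroke or death from any cause* in SAP 1.2.2, Table 1, 3.3 and 6.2.2, and align the protocol at its next amendment.
4. Add a supportive analysis on the written definition, counting index-stroke deaths only. Take the cause from the fatal SAE report by a blinded, pre-specified rule that also covers deaths with no usable cause, such as those found in public sources (protocol 7.3).
5. In 6.2.2, note that participants who died without imaging are already events under 4.3.

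The cost is a SAP revision, a protocol amendment that needs ethics approval (protocol 10.1.1), and one extra analysis. A SAP revision is due in any case: SAP 1.3 and 1.4 still plan 680 to 1020 participants with sample size re-estimation, against 850 in the protocol. Reported deaths need no new data, since protocol 10.3.2 has all deaths to Day 90 reported as SAEs. The supportive analysis will carry some misclassification, because no cause-of-death adjudication is described and the fatal SAE may name a condition that only contributed.
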